3. OBJECTIVES

The objectives of this study are:

1. To demonstrate non-inferiority of BPL HRIG compared to an FDA-licensed HRIG product, in terms of the proportion of subjects achieving anti-rabies antibody titer of ≥ 0.5 IU/mL at Day 14 following treatment with HRIG in conjunction with active rabies vaccine.
2. To compare the PK of BPL HRIG in conjunction with active rabies vaccine, with FDA-licensed HRIG product in conjunction with active rabies vaccine.
3. To assess whether BPL HRIG interferes with the development of the host-immune response when given simultaneously with active rabies vaccine, relative to an FDA-licensed HRIG product
4. To evaluate the safety and tolerability of BPL HRIG in comparison with FDA-licensed HRIG product.

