6. INVESTIGATIONAL AND AUXILIARY MEDICINAL PRODUCTS

In this study, 'study medication' is defined as all products administered: BPL HRIG, comparator HRIG, and active rabies vaccine.

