10.6.1. Adverse Events

Adverse events (AEs) will be reported by the MedDRA system organ class and preferred term. Only treatment-emergent AEs, defined as those events with onset date from dosing with BPL HRIG / vaccine or comparator HRIG / vaccine will be included in the summary tables. All AEs will be included in the data listings.

Treatment-related AEs will be defined as events recorded as having a possible, probable or very likely/certain causality to treatment. AEs leading to withdrawal will be defined as events where the subject's participation in the study was discontinued as a result of the AE.

AEs will be summarized descriptively for all subjects and by treatment group. The denominator used for the calculation of percentages will be the number of subjects in the safety population per treatment group. For all AE summaries described below, counting will be performed by subject and event. For counts by subject, subjects experiencing the same event more than once

will have that event counted only once within each system organ class and once within each preferred term.

The following summaries of treatment-emergent AEs will be provided:

Summary of AEs

- 1) The number and percentage of subjects reporting AEs, serious AEs, study medication related AEs, AEs leading to withdrawal and AEs leading to death.
- 2) The number of AEs, serious AEs, study medication-related AEs, AEs leading to withdrawal and AEs leading to death.

Summary of AEs by Severity of Event

The number and percentage of subjects reporting AEs, and study medication-related AEs, will be summarized by the system organ class and by the preferred term. The severity of event will be recorded once per subject for each term as the maximum severity experienced by each subject (i.e. where the order of most severe to least severe is given by: severe, moderate and then mild).

Summary of AEs by Causality

The number and percentage of subjects reporting AEs will be summarized by the system organ class and by the preferred term. The causality will be recorded once per subject for each term giving the most likely relationship to study medication (i.e. in the order: very likely/certain, probable, possible, unlikely and then unrelated).

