3.1 Causality

All AEs will be recorded in the CRF/eCRF, whether considered to be related or unrelated to the treatment. The record will include the following: brief description of event (preferably a diagnosis), date and time started and stopped severity, outcome, actions taken and classification of the AE. The Investigator should also evaluate the probability of a causal relationship of the AE to each medication administered during the study according to the following criteria as:

-
1. Unrelated Clinical event with an incompatible time relationship to study medication administration, or that could be explained by underlying disease or other drugs or chemicals, or is incontrovertibly not related to the IMP.
 2. Unlikely Clinical event whose time relationship to study medication administration makes a causal connection improbable, but that could plausibly be explained by underlying disease or other drugs or chemicals.
 3. Possible Clinical event with a reasonable time relationship to study medication administration, but that could also be explained by concurrent disease or other drugs or chemicals.
 4. Probable Clinical event with a reasonable time relationship to study medication administration, and is unlikely to be attributed to concurrent disease or other drugs or chemicals.
 5. Very likely / certain Clinical event with plausible time relationship to study medication administration, and that cannot be explained by concurrent disease or other drugs or chemicals.

Study medication is defined as those investigational compounds or their controls and vaccines used in the study.

It will be assumed that for all adverse events classified as “probably related”, “possibly related” or “very likely / certainly related” to the study medication, there is reasonable likelihood that the adverse event was causally related to the product. All such adverse events will be regarded as “causally related” to the study medication.

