- The number and percentage of subjects reporting AEs, serious AEs, study medication-related AEs, AEs leading to withdrawal and AEs leading to death.
- The number of AEs, serious AEs, study medication-related AEs, AEs leading to withdrawal and AEs leading to death.

SUMMARY OF AEs BY SEVERITY OF EVENT

The number and percentage of subjects reporting AEs, and study medication-related AEs, will be summarized by the system organ class and by the preferred term. The severity of event will be recorded once per subject for each term as the maximum severity experienced by each subject (i.e. where the order of most severe to least severe is given by: severe, moderate and then mild).

SUMMARY OF AEs BY CAUSALITY

The number and percentage of subjects reporting AEs will be summarized by the system organ class and by the preferred term. The causality will be recorded once per subject for each term giving the most likely relationship to study medication (i.e. in the order: very likely/certain, probable, possible, unlikely and then unrelated).

i. SENSITIVITY ANALYSES

Sensitivity analyses will be performed to assess the impact on the primary PK analysis of non-compliers within the ITT population, missing primary endpoints, and timing of vaccine dosing.

POTENTIAL INTERACTION

Before treatment unblinding, timing of vaccine dosing and PK sampling, if not performed on the designated day, will be assessed as potential effect modifiers on the association between RVNA levels and treatment group in the primary and secondary PK analysis. A chi-square or fisher's exact test, as appropriate, will be used to measure the association between the dichotomous indicator of receiving dose/PK sampling on the intended day

[yes/no] and target level of RVNA titer reached [yes/no]. If the association is significant at the 0.05 level, a subgroup analysis including only subjects who were dosed/sampled on the target day will be reported in addition to the full analysis.

NON-COMPLIERS AND MISSING DATA

Non-compliers will be defined as subjects who meet one of the following:

- subjects who did not receive the full dose of BPL HRIG/comparator HRIG [not eligible for primary PK population];
- all 3 doses of active rabies vaccine at the time specified [not eligible for primary PK population];
- randomized without meeting all eligibility criteria [REDACTED];
- subjects with any major protocol deviations reported [REDACTED].

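### Causality is to be rated per product, but related AEs are tabulated only against HRIG and vaccine pooled, which dilutes the subject-level related-AE comparison between the two HRIGs

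*Protocol*

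**What the plan says.** **Collection.** Protocol Appendix A 3.1 has the investigator "evaluate the probability of a causal relationship of the AE to each medication administered during the study", on a five-grade scale.

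**Definition.** Protocol section 6 says that study medication "is defined as all products administered: BPL HRIG, comparator HRIG, and active rabies vaccine". Appendix A 3.1 pools in the same way: "Study medication is defined as those investigational compounds or their controls and vaccines used in the study".

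**Reporting.** Protocol 10.6.1 counts subjects and events with study-medication-related AEs, and defines relatedness without naming a product: "Treatment-related AEs will be defined as events recorded as having a possible, probable or very likely/certain causality to treatment". For the by-causality table, "The causality will be recorded once per subject for each term giving the most likely relationship to study medication". SAP 8.h uses the same rule, "giving the most likely relationship to study medication". All these summaries are by treatment group.

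**Where products are separated.** Injection site reactions are summarized separately for HRIG and vaccine (protocol 10.6.2 and the SAP's injection site section). No other planned safety table is split this way.

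**Purpose.** Objective 4 is "To evaluate the safety and tolerability of BPL HRIG in comparison with FDA-licensed HRIG product".

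**The concern.** Objective 4 concerns the two immunoglobulins, while the related-AE columns mix one HRIG administration with five vaccine doses. Vaccine-attributed events raise both columns by a common background and pull the arms together. The expected reactions overlap: protocol Table 3 lists headache, fever, malaise and fatigue as HRIG class effects, and protocol 2.8 lists the same four among the vaccine's common reactions. The background is therefore likely to be heaviest in the systemic terms the products share.

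The protocol says that BPL HRIG has had no clinical trials (2.5) and that this study supports a US license application (2.9). As planned, no summary table would give the frequency of non-injection-site AEs that investigators attributed to BPL HRIG. Because the safety review is descriptive (protocol 10.6), it depends on the visible size of a contrast.

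**Working it through.** **1. No figure of the plan's own to reproduce.** The documents give no related-AE rate, no safety margin and no safety sample size. The primary-endpoint sample size, alpha and power are unaffected.

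**2. How one event is counted.** Take an AE rated unrelated to HRIG and very likely/certain for vaccine. Neither document says how two product ratings on one event become one. With study medication defined as the pool, and the strongest relationship kept per subject and term, the natural reading is that the event enters the table as very likely/certain and counts as related.

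**3. Subject-level dilution.** Let h be the proportion of subjects with an HRIG-related AE and v the proportion with a vaccine-related AE, with v equal in both arms (same schedule, protocol 6.2) and independent of h. Then:

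- pooled related rate = 1 - (1-v)(1-h)
- pooled risk difference = (1-v) × (difference in h)

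Both h and v are assumptions. For h = 10% versus 20%:

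| v | Pooled rates | Risk difference | Risk ratio |
|---|---|---|---|
| 0% (HRIG-related only) | 10% vs 20% | 10 points | 2.00 |
| 2% | 11.8% vs 21.6% | 9.8 points | 1.83 |
| 30% | 37% vs 44% | 7 points | 1.19 |
| 50% | 55% vs 60% | 5 points | 1.09 |
| 70% | 73% vs 76% | 3 points | 1.04 |

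Example for v = 30%: 1 - 0.7 × 0.9 = 0.37 and 1 - 0.7 × 0.8 = 0.44.

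The factor (1-v) does not depend on h. For 10% versus 30%, the 20-point difference becomes 14, 10 and 6 points at v = 30%, 50% and 70%. For 1% versus 2%, the 1-point difference becomes 0.7, 0.5 and 0.3 points. The factor is positive for v below 1, so the direction is kept. If the same subjects tend to have both kinds of event, dilution is stronger than shown; if they tend not to, it is weaker.

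**4. Term-level tables.** In the system organ class and preferred term tables, v is the vaccine rate for that class or term. The 2% row stands for a term the vaccine rarely causes: almost nothing is lost.

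**5. Event counts.** Protocol 10.6.1 also counts events. If each event is attributed to one product, expected counts add. With assumed HRIG-related means of 0.10 and 0.20 events per subject and a vaccine mean of 0.50 in both arms, the totals are 0.60 and 0.70. The absolute difference stays 0.10, while the ratio falls from 2.00 to 0.70/0.60 = 1.17.

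**The case against.** The strongest reply is that randomization already does the work. Every AE summary is by arm and the vaccine schedule is identical, so an imbalance in all-cause AEs points to the HRIG without any causality rating. This stands. A reader might infer that pooling hides any HRIG difference; the documents do not support that. The by-arm tables would still show an excess, in the same direction though reduced at subject level, and local reactions are split by product. The all-cause tables do carry the vaccine background plus unrelated events, so they do not remove the dilution.

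Second, protocol 8.2 and SAP section 6 frame the safety assessment as HRIG with vaccine against comparator HRIG with vaccine. This also stands. The pooled column is labelled study medication and does not claim attribution to BPL HRIG, so it would be wrong to say that it misstates the HRIG's rate.

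Third, attribution is subjective. HRIG and the first vaccine dose are given consecutively on Day 0 (protocol 7.3.2), and their systemic effects overlap. A reader might conclude that HRIG-related AEs should become the main comparison between arms. They should not: that would rank a judgment-based classification above the randomized one. As supplementary tables the ratings still inform, since four of the five vaccine doses are given on later days without HRIG and AE assessors are blinded.

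Fourth, the assumed rates have no anchor. Table 3 grades HRIG class effects as rare, below 1 in 1,000. At that frequency, 81 subjects would give fewer than 81 × 0.001 = 0.081 expected cases per term, and no table would show a difference.

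Finally, separate product ratings rest on one sentence in Appendix A 3.1. The grade definitions beneath it refer to study medication or the IMP, the SAE form content (Appendix A 5.1) asks for causality to study medication, and the eCRF is not in the documents.

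**Conclusion.** The point holds as a reporting gap. Causality is to be rated per product, but related AEs are tabulated only against the pool. The ratings therefore feed no planned summary, and products are separated only for injection site reactions. The subject-level related-AE contrast between the HRIGs is diluted by the factor (1-v): a 30% to 70% loss of the risk difference if v lies between 30% and 70%, and little loss for terms the vaccine rarely causes. This rests on independence, an equal v in both arms and assumed rates. Pooling does not reverse the difference, and absolute differences in event counts are preserved. No safety hypothesis test is planned, so no decision rule is affected. The change is worth making because it is cheap and bears directly on Objective 4.

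**What to change.** - Confirm that the eCRF holds separate causality fields for HRIG and vaccine. If it does not, reconcile it with Appendix A 3.1.
- In protocol 10.6.1 and SAP 8.h, define HRIG-related and vaccine-related treatment-emergent AEs from those ratings, and state how two ratings on one event combine into the pooled rating.
- Add supplementary by-arm summaries of each: overall, by severity and by causality.
- Keep the all-cause by-arm tables as the main randomized safety comparison, and keep the pooled related-AE table.
- Note in the SAP that attribution is uncertain for AEs soon after Day 0.

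If the separate fields exist, the cost is SAP wording and a few repeat tables, with no new data or subjects. The drawback is more tables, some resting on uncertain early attribution.

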10.6.2. Injection Site Observations

Injection site observations data will be summarized as appropriate.

Summary by Product

The number and percentage of subjects reporting injection site reactions will be summarized by preferred term and product (HRIG or vaccine).

Summary by Number of Injections

The number and percentage of subjects reporting injection site reactions will be summarized by preferred term, product (HRIG or vaccine) and number of injections.

10.6.3. Viral Serology Variables

Viral serology variables will be summarized. Shift tables for virology will present the number of subjects with positive and negative results and those for whom the results change during the study.

10.6.4. Hematology, Serum Biochemistry, Urinalysis

Hematology, serum biochemistry and urinalysis variables will be summarized, including changes from baseline.

Shift tables for hematology and biochemistry variables will be provided for the number and percentage of subjects with values below, within and above the reference range.

10.6.5. Markers of Hemolysis

Markers of hemolysis will be summarized, including changes from baseline.

10.6.6. Vital Signs and Body Temperature

Sitting diastolic and systolic blood pressure, pulse rate, body temperature and respiration rate will be summarized, including changes from baseline (i.e. pre-dose on Visit 2 for body temperature, Screening for all other parameters). In addition, the number of subjects with “substantial” increases or decreases from baseline in blood pressure (>20 mmHg) and pulse (>15 bpm) will be summarized.

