7.2. Visit 1: Screening Visit (up to Day -28)

The screening visit may be performed up to 28 days before first dose of investigational product.

The following assessments will be performed:

- Medical history, concomitant medications check
- Demography, gender
- Physical examination including 12-lead ECG, height and body weight
- Vital signs: sitting blood pressure (mmHG) after a 5-min rest, pulse rate and respiration rate
- Blood samples will be taken for the following assessments:
 - o virology: anti-HIV1&2, HBsAg, anti-HCV (see [Section 8.2.3](#))
 - o serum biochemistry (see [Section 8.2.3](#))
 - o hematology (see [Section 8.2.5](#))
 - o serum pregnancy test for all females of child-bearing potential
- Reserve blood samples will be taken (see [Section 7.9.1](#))
- A urine sample will be collected for urinalysis (see [Section 8.2.6](#)).

There will be a review of eligibility criteria. At the investigator's discretion, one or more screening laboratory tests may be repeated prior to Day 0 (Visit 2) and if not clinically significant and otherwise qualifying to determine eligibility.

For full details of sample collection, labeling, processing and storage for all laboratory tests please see the separate Laboratory Manual.

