7.3.1. Before Dosing (Day 0)

The following procedures will be performed prior to dosing:

- Review of continued eligibility, including:
 - o elements of informed consent
 - o interim medical history
 - o concomitant medications
 - o Vital Signs
- Oral temperature. If the participant is febrile (oral temperature >38.0°C [100.4°F]) or has an acute illness, their enrollment must be re-scheduled. The decision to delay vaccinations because of a current or recent acute illness depends on the severity of the symptoms and their cause. Although a moderate or severe acute illness is sufficient reason to postpone vaccination, minor illnesses are not necessarily contraindications to vaccination. If re-scheduled, Day 0 must be within 28 days of all screening procedures; if greater than 28 days the subject must undergo a repeat screening visit. A new subject number will be assigned for repeat screening visits (see Study Reference Manual (SRM) for instructions on repeat screening).
- Body weight will be measured for reassessment of eligibility and calculation of the dose of HRIG in IU/kg
- A urine pregnancy test in females of childbearing potential
- A urine sample will be taken for urine hemosiderin (see [Section 8.2.7](#))
- Blood samples will be taken for the following assessments:
 - o rabies virus neutralizing antibodies (see [Section 8.1.4](#))
 - o markers of hemolysis (DCT, LDH, plasma free hemoglobin, serum haptoglobin and serum bilirubin) (see [Section 8.2.7](#))
- Reserve blood samples will be taken (see [Section 7.9.1](#))
- An archive serum sample will be taken (see [Section 7.9.2](#)) for long-term storage at -70°C for approximately 15 years.

The subject will then be randomized to treatment Group A or B, as described in [Section 6.2](#) .

7.3.2. Dosing on Day 0

Immediately prior to dosing, each injection site for the HRIG will be examined for pain, tenderness, erythema and induration (see [Section 8.2.2](#)) by the blinded site personnel, to establish a baseline for local tolerance.

According to the subject's randomized treatment, an IM injection of 20 IU/kg body weight BPL HRIG or HyperRAB® S/D will be administered. This will be followed by an IM injection of 1.0 ml licensed active rabies vaccine. Treatments for injection will be prepared and administered by unblinded site staff, who will remain separate to the study team as described in [Section 6.6](#).

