8.2.8. Vital Signs and Body Temperature

Vital signs will be assessed at Screening, Day 0, Day 28, and Day 49 and at the End-of-Study Assessment. Vital signs will include the following assessments:

- Sitting blood pressure (mmHg) after a 5-min rest.
- Pulse rate (bpm).
- Respiration rate (breaths/respirations per minute).

Results at the Screening Visit will be used to determine eligibility for the study. Evidence of uncontrolled hypertension (systolic blood pressure of >150 mmHg, and/or diastolic blood pressure of >100 mmHg), or heart rate >120 beats/min will exclude the subject from the study.

Oral body temperature will be assessed pre-dose on Days 0, 3, 7, 14 and 28. If the subject is febrile (oral temperature $>38.0^{\circ}\text{C}$ [100.4°F]) or has an acute illness at Day 0, their enrollment must be re-scheduled (see [Section 7.3.1](#)). If re-scheduled, Day 0 must be within 28 days of all screening procedures; if outside of this window the subject must undergo a repeat screening visit. A new subject number will be assigned. (See SRM for instructions on repeat screening).

If the subject is febrile at any subsequent visit, active rabies vaccine must not be given. The subject may continue in the study but should receive no further doses of active rabies vaccine and will not be eligible for the per protocol population.

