10.6. Safety Analysis

The safety analysis will be based on the safety population. The general strategy of the safety evaluation will be to examine the summaries for any clinically relevant imbalance of safety events between the treatment groups. Safety parameters for the two treatment groups will be compared descriptively. Summary data will be presented by Treatment Group. No formal hypothesis testing will be carried out.

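### Changes in blood pressure, pulse and respiration are measured from Screening although a pre-dose Day 0 value is collected, so change before treatment enters the scores and the 'substantial' change counts.

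*Protocol*

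**What the plan says.** Protocol 10.6.6 summarizes sitting blood pressure, pulse, respiration rate and temperature with changes from baseline, and defines that baseline as "pre-dose on Visit 2 for body temperature, Screening for all other parameters". SAP 8.p repeats the rule. Both sections also count subjects with substantial "increases or decreases from baseline in blood pressure (>20 mmHg) and pulse (>15 bpm"). The count uses the same baseline and names no visits.

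On timing, Protocol 7.2 states: "The screening visit may be performed up to 28 days before first dose of investigational product". Protocol 8.2.8 gives the schedule: "Vital signs will be assessed at Screening, Day 0, Day 28, and Day 49 and at the End-of-Study Assessment". The Day 0 reading is taken before dosing. Protocol 7.3.1 lists vital signs in a section that opens "The following procedures will be performed prior to dosing", and the flow charts in Protocol Appendix G and SAP 5 mark them in the pre-dose column of Visit 2.

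Protocol 10.6 makes the safety comparison descriptive: "No formal hypothesis testing will be carried out". Neither document says why Screening is preferred to Day 0 for these three measurements.

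**The concern.** A change-from-baseline table for safety is read as change since treatment. Here the reference reading can be four weeks older than the first dose, while a reading from the dosing visit itself is available. Two things follow.

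- Any movement between Screening and Day 0, which no study product can have caused, is carried into the change score at every later visit.
- Day 0 is a scheduled assessment after the baseline, and the substantial-change count is not limited to post-dose visits. As written, a subject whose blood pressure moved by more than 20 mmHg before receiving anything could be counted.

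For adverse events the plan guards against this: Protocol 10.6.1 keeps events with onset before dosing out of the summary tables. The vital-sign section has no such limit. What is at stake is how clearly a descriptive safety table can be read, not any confirmatory conclusion.

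**Working it through.** **Texts side by side.** Protocol 10.6.6 and SAP 8.p agree on Screening as the baseline. Protocol 7.3.1, 8.2.8, Appendix G and SAP 5 agree that a pre-dose Day 0 value exists. Elsewhere the plan uses the word baseline for Visit 2: Protocol 7.3 calls it the Baseline Visit, the visit table in SAP 7 labels it so, and the repeated-measures titer model in SAP 8.f takes it as the starting point.

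**Longest interval from baseline to each post-dose reading.** Inputs: a screening window of 28 days (Protocol 7.2) and visit windows of ±2, ±4 and ±7 days (Appendix G). The figure in brackets is at the late edge of the window.

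| Visit | From Screening | From Day 0 |
|---|---|---|
| Day 28 | 28 + 28 = 56 (58) | 28 (30) |
| Day 49 | 28 + 49 = 77 (81) | 49 (53) |
| Day 140 | 28 + 140 = 168 (175) | 140 (147) |

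The 175 days agree with the 25-week maximum in Protocol 4.6 (25 × 7 = 175). From baseline to dosing, the gap is up to 28 days under the stated rule and nil with Day 0.

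**What enters the score.** For a later visit,

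visit − Screening = (Day 0 − Screening) + (visit − Day 0).

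The first bracket is entirely pre-treatment. At Day 0 itself the second bracket is zero, so a change reported or counted there is wholly pre-treatment.

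**Size: illustration only.** The documents give no SD and no within-subject correlation. Assume normal values with the same SD s at both readings, correlation r between them, and no true effect. Then SD of change = s√(2(1 − r)), and the chance that the absolute change exceeds a threshold t is 2[1 − Φ(t / SD of change)]. With 81 subjects per arm:

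| Measure and threshold | Assumed s | r = 0.5 | r = 0.8 |
|---|---|---|---|
| Blood pressure, 20 mmHg | 15 | SD 15.0; 18.2%; 14.8 of 81 | SD 9.49; 3.5%; 2.8 of 81 |
| Blood pressure, 20 mmHg | 10 | SD 10.0; 4.6%; 3.7 of 81 | SD 6.32; 0.2%; 0.1 of 81 |
| Pulse, 15 bpm | 12 | SD 12.0; 21.1%; 17.1 of 81 | SD 7.59; 4.8%; 3.9 of 81 |
| Pulse, 15 bpm | 8 | SD 8.0; 6.1%; 4.9 of 81 | SD 5.06; 0.3%; 0.2 of 81 |

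If r is read as the Screening-to-Day 0 correlation, these are the numbers that could be flagged before any product is given, from almost none to about 17 per arm. The table shows that the counts are sensitive to the assumptions. It does not measure the difference between the two baselines. By the same formula, Screening gives noisier changes than Day 0 only if it correlates less well with the later visits, and the documents have no data on that.

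**The case against.** The rule is explicit, prespecified and identical in both documents. Screening is also the reference for the physical examination and ECG shifts (Protocol 10.6.7), and it is the only scheduled pre-dose point for hematology, biochemistry and urinalysis, so using it for vital signs is consistent with the rest of the safety plan. No vital signs are scheduled between dosing and Day 28. Even from Day 0, then, the changes span about 28, 49 and 140 days and include ordinary within-subject variation. All data are listed (Protocol 10.3), so anyone can derive a Day 0 change. Randomization is 1:1, assessors are blinded and the rule does not differ by arm.

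Most of this stands, and it limits the point to a minor one. It does not supply a reason to prefer the older reading when a pre-dose one exists. A listing also does not correct a summary count that can include pre-dose shifts.

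A reader might infer two further arguments, which the documents do not support.

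- **Regression to the mean.** Screening readings decide eligibility, so they might look selected in a way that Day 0 readings are not. But Protocol 7.3.1 places the Day 0 vital signs under the repeat eligibility check, and the blood-pressure and heart-rate exclusions in Protocol 5.3 are not tied to Screening. Day 0 is not free of selection either.
- **Inconsistency with body temperature.** Temperature uses Day 0, which might look like a conflicting choice. But no temperature is scheduled at Screening, so Day 0 is the only planned pre-dose value.

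**Conclusion.** The point holds as a minor weakness in a definition. Change in blood pressure, pulse and respiration is measured from a reading up to 28 days before dosing although a pre-dose Day 0 reading is collected, and the substantial-change counts can include shifts that arose before treatment.

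The effect is non-differential noise in a descriptive safety table. A reader might infer that the rule biases the comparison between arms or weakens the non-inferiority result. The documents do not support this: the same rule applies to both randomized, blinded arms, vital signs are not formally tested, and neither the Day 14 titer endpoint nor the sample size uses them. Nor is this a contradiction between Protocol and SAP, which agree.

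No magnitude can be derived from the documents. The 28 days is the maximum width of a window, not an amount of drift, and the illustrative counts rest entirely on the assumed SDs and correlations.

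**What to change.** Make the same two edits in Protocol 10.6.6 and SAP 8.p.

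1. Define baseline for every vital sign as the last non-missing value before the first product is given: the pre-dose Day 0 value, or Screening if that is missing. For temperature nothing changes in practice.
2. State that the counts of changes above 20 mmHg and 15 bpm cover assessments after dosing only. The Screening-to-Day 0 change can still be shown as a separate descriptive row.

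If the sponsor wishes to keep Screening as the baseline, give the reason and still make the second edit.

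The cost is a sentence or two in each document and one changed derivation in the programming, settled before unblinding. No new data, visits, samples or subjects are needed.
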